5.6.18. Study conclusion

The investigator will:

- review data collected to ensure accuracy and completeness.
- complete study conclusion screen in the eCRF.

5.7. Biological sample handling and analysis

Please refer to the SPM and Central Laboratory Manual for details on biospecimen management (handling, storage and shipment).

Samples will not be labelled with information that directly identifies the subject but will be coded with the identification number for the subject (subject number).

- Collected samples will be used for protocol mandated research and purposes related to the improvement, development and quality assurance of the laboratory tests described in this protocol. This may include the management of the quality of these

tests, the maintenance or improvement of these tests, the development of new test methods, as well as making sure that new tests are comparable to previous methods and work reliably.

- It is also possible that future findings may make it desirable to use the samples acquired in this study for future research, not described in this protocol. Therefore, all subjects in countries where this is allowed, will be asked to give a specific consent to allow GSK or a contracted partner to use the samples for future research. Future research will be subject to the laws and regulations in the respective countries and will only be performed once an independent Ethics Committee or Review Board has approved this research.

Information on further investigations and their rationale can be obtained from GSK Biologicals.

Any sample testing will be done in line with the consent of the individual subject.

Refer also to the [Investigator Agreement](#), where it is noted that the investigator cannot perform any other biological assays except those described in the protocol or its amendment(s).

Collected samples will be stored for a maximum of 20 years (counting from when the last subject performed the last study visit), unless local rules, regulations or guidelines require different timeframes or different procedures, which will then be in line with the subject consent. These extra requirements need to be communicated formally to and discussed and agreed with GSK Biologicals.

5.7.1. Use of specified study materials

When materials are provided by GSK Biologicals *or by the Central laboratory*, it is MANDATORY that all clinical samples (including serum samples) be collected and stored exclusively using those materials in the appropriate manner. The use of other materials could result in the exclusion of the subject from the ATP analysis (See Section [10.4](#) for the definition of cohorts to be analysed). The investigator must ensure that his/her personnel and the laboratory(ies) under his/her supervision comply with this requirement. However, when GSK Biologicals does not provide material for collecting and storing clinical samples, appropriate materials from the investigator's site must be used. Refer to the Module on Clinical Trial Supplies in the SPM. **(Amended 16 March 2016)**

5.7.2. Biological samples

Table 8 Biological samples

| Sample type | Quantity | Unit | Time point | Sub-cohort |
|--|----------|------|-----------------------------|-----------------------|
| Blood for safety assessment | ~5.5 | mL | Screening Visit (pre-Day 0) | All screened subjects |
| | | | Visit 1 (Day 0) | All enrolled subjects |
| | | | Visit 2 (Day 7) | |
| | | | Visit 4 (Day 60) | |
| | | | Visit 5 (Day 67) | |
| | | | Visit 7 (Day 210) | |
| | | | Visit 8 (Day 420) | |
| | | | | |
| Blood for antibody determination and assay development | ~20 | mL | Visit 1 (Day 0)) | All enrolled subjects |
| | | | Visit 3 (Day 30) | |
| | | | Visit 4 (Day 60) | |
| | | | Visit 6 (Day 90) | |
| | | | Visit 7 (Day 210) | |
| | | | Visit 8 (Day 420) | |
| Blood for CMI response | ~20 | mL | Visit 1 (Day 0)) | Sub-cohort for CMI* |
| | | | Visit 4 (Day 60) | |
| | | | Visit 6 (Day 90) | |
| | | | Visit 7 (Day 210) | |
| | | | Visit 8 (Day 420) | |

* Refer to Section 4.1 for sub-cohort description.

5.7.3. Laboratory assays

Please refer to [APPENDIX A](#) for a detailed description of the assays performed in the study. Please refer to [APPENDIX B](#) for the address of the clinical laboratories used for sample analysis.

Haematology and biochemistry

Haematology and biochemistry assays for safety assessment will be performed in a central laboratory (refer to [Table 9](#)).

Table 9 Haematology and biochemistry tests

| System | Discipline | Component | Method | Scale | Laboratory** |
|-------------|--------------|----------------------------------|--------------------------------------|--------------|--------------------|
| Whole blood | Haematology | Leukocytes (White Blood Cells) | Per contract laboratory's procedures | Quantitative | Central laboratory |
| | | Neutrophils* | Per contract laboratory's procedures | Quantitative | |
| | | Lymphocytes* | Per contract laboratory's procedures | Quantitative | |
| | | Basophils* | Per contract laboratory's procedures | Quantitative | |
| | | Monocytes* | Per contract laboratory's procedures | Quantitative | |
| | | Eosinophils* | Per contract laboratory's procedures | Quantitative | |
| | | Haemoglobin | Per contract laboratory's procedures | Quantitative | |
| | | Platelets | Per contract laboratory's procedures | Quantitative | |
| | | Erythrocytes (Red Blood Cells) | Per contract laboratory's procedures | Quantitative | |
| Serum | Biochemistry | Alanine Aminotransferase (ALT) | Per contract laboratory's procedures | Quantitative | Central laboratory |
| | | Aspartate Aminotransferase (AST) | Per contract laboratory's procedures | Quantitative | |
| | | Creatinine | Per contract laboratory's procedures | Quantitative | |

* For White Blood Cell (WBC) differential count.

** Refer to [Table 25](#) for the laboratory address.

Humoral immune responses

Serological assays for the quantification of antibodies will be performed by ELISA at GSK Biologicals' laboratory or in a laboratory designated by GSK Biologicals using standardised procedures (refer to [Table 10](#)).

Table 10 Humoral Immunity (antibody determination) (Amended 16 March 2016)

| System | Component | Method | Kit / Manufacturer | Unit | Cut-off | Laboratory* |
|--------|------------|--------|--------------------|---------|---------|-------------------|
| Serum | Anti-PD | ELISA | In house | EL.U/mL | 153 | GSK Biologicals** |
| Serum | Anti-PE | ELISA | In house | EL.U/mL | 8 | GSK Biologicals** |
| Serum | Anti-PilA | ELISA | In house | EL.U/mL | 7 | GSK Biologicals** |
| Serum | Anti-UspA2 | ELISA | In house | EL.U/mL | 18 | GSK Biologicals** |

ELISA: Enzyme-Linked Immunosorbent Assay; EL.U/mL = ELISA unit per millilitre;

* Refer to [APPENDIX B](#) for the laboratory addresses.** GSK Biologicals laboratory refers to the **Clinical Laboratory Sciences (CLS) Laboratories** in Rixensart, Belgium; Wavre, Belgium or a designated laboratory.

Serum samples might also be used for **development and validation of other assays** to measure the immune response to components of either the NTHi-Mcat investigational vaccines and/or of other respiratory pathogens such as, but not limited to, serum bactericidal activity assay, anti-PD, -PE, -PilA, -UspA2 functional assays, immunochemistry assays for other immunoglobulin classes and/or for anti-IgG subclasses, and anti-AS01_E assays. Hence, additional use and/or testing of serum samples may occur during the course of the study or after study completion in case these data should be required for accurate interpretation of the study results and/or for further research related to the vaccine and/ or the disease and/ or should such test(s) become available at GSK Biologicals' laboratory or a laboratory designated by GSK Biologicals.

Cell-mediated immune responses

CMI assays will be performed at GSK Biologicals' laboratory using standardised procedures (refer to [Table 11](#)). Plasma collected during the processing of peripheral blood mononuclear cells (PBMCs) will be stored for potential future analyses and/or for assay development purposes.

Table 11 Cell-Mediated Immunity (CMI) (Amended 16 March 2016)

| System | Component | Scale | Method | Unit | Laboratory* |
|--------|---|--------------|----------------|--|-------------------|
| PBMC | Specific CD4 ⁺ /CD8 ⁺ T-cells | Quantitative | Flow cytometry | Number of specific CD4 ⁺ /CD8 ⁺ T cells /10 ⁶ | GSK Biologicals** |

PBMC = peripheral blood mononuclear cell.

* Refer to [APPENDIX B](#) for the laboratory addresses.** GSK Biologicals laboratory refers to the **Clinical Laboratory Sciences (CLS) Laboratories** in Rixensart, Belgium; Wavre, Belgium or a designated laboratory.

Additional testing on PBMCs, such as, but not limited to, evaluation of NTHi- and Mcat-specific memory B-cells and intracellular cytokine staining (ICS) using other microbial antigens, may be done during the study or after study completion, should these data be required for accurate interpretation of the data and/ or for further research related to the investigational vaccine and/ or the disease and/ or should such test(s) become available at GSK Biologicals' laboratory or a laboratory designated by GSK Biologicals.

The GSK Biologicals' clinical laboratories have established a Quality System supported by procedures. The activities of GSK Biologicals' clinical laboratories are audited regularly for quality assessment by an internal (sponsor-dependent) but laboratory-independent Quality Department.

5.7.4. Biological samples evaluation

5.7.4.1. Immunological read-outs

Table 12 Immunological read-outs

| Blood sampling time point | | Sub-cohort Name | No. subjects | Component |
|--------------------------------|---------------------|-----------------|--------------|---|
| Type of contact and time point | Sampling time point | | | |
| Visit 1 (Day 0) | Pre-Vacc | All subjects | ~120 | Anti-PD, Anti-PE, Anti-PilA and Anti-UspA2 |
| | | CMI sub-cohort* | ~45 | Specific CD4 ⁺ /CD8 ⁺ T-cells |
| Visit 3 (Day 30) | Post-Vacc I | All subjects | ~120 | Anti-PD, Anti-PE, Anti-PilA and Anti-UspA2 |
| Visit 4 (Day 60) | Post-Vacc I | All subjects | ~120 | Anti-PD, Anti-PE, Anti-PilA and Anti-UspA2 |
| | | CMI sub-cohort* | ~45 | Specific CD4 ⁺ /CD8 ⁺ T-cells |
| Visit 6 (Day 90) | Post-Vacc II | All subjects | ~120 | Anti-PD, Anti-PE, Anti-PilA and Anti-UspA2 |
| | | CMI sub-cohort* | ~45 | Specific CD4 ⁺ /CD8 ⁺ T-cells |
| Visit 7 (Day 210) | Post-Vacc II | All subjects | ~120 | Anti-PD, Anti-PE, Anti-PilA and Anti-UspA2 |
| | | CMI sub-cohort* | ~45 | Specific CD4 ⁺ /CD8 ⁺ T-cells |
| Visit 8 (Day 420) | Post-Vacc II | All subjects | ~120 | Anti-PD, Anti-PE, Anti-PilA and Anti-UspA2 |
| | | CMI sub-cohort* | ~45 | Specific CD4 ⁺ /CD8 ⁺ T-cells |

* Approximately 50% of the subjects in each group of the Step 2 will be part of a sub-cohort for CMI analysis.

5.7.4.2. Haematology and biochemistry

Table 13 Haematology/ biochemistry

| Blood sampling time point | | Sub-cohort Name | No. subjects | Component |
|--------------------------------|---------------------|-----------------|--------------|--|
| Type of contact and time point | Sampling time point | | | |
| Screening* (Pre-Day 0) | Screening | All subjects | ~120 | Haematology (leukocytes [white blood cells], white blood cell differential count [neutrophils, lymphocytes, eosinophils, basophils, monocytes], erythrocytes [red blood cells], haemoglobin, platelets) |
| Visit 1 (Day 0) | Pre-Vacc I | All subjects | ~120 | |
| Visit 2 (Day 7) | Post-Vacc I | All subjects | ~120 | |
| Visit 4 (Day 60) | Post-Vacc I | All subjects | ~120 | |
| Visit 5 (Day 67) | Post-Vacc II | All subjects | ~120 | |
| Visit 7 (Day 210) | Post-Vacc II | All subjects | ~120 | Biochemistry (ALT, AST, creatinine) |
| Visit 8 (Day 420) | Post-Vacc II | All subjects | ~120 | |

ALT: Alanine aminotransferase; AST: Aspartate aminotransferase

Screening evaluations may be completed 1 to 28 days before Day 0. Site staff should allow sufficient time between the Screening and Day 0 visits to receive and review screening safety laboratory test results. If a delay occurs such that the interval between Screening and the Day 0 vaccination exceeds 28 days, a re-screening visit should be scheduled before Visit 1 during which blood sample collection for safety laboratory assessment should be repeated.

5.7.5. Immunological correlates of protection

No generally accepted immunological correlate of protection has been demonstrated so far for the antigens used in the investigational vaccines.

6. STUDY VACCINES AND ADMINISTRATION

6.1. Description of study vaccines

All candidate vaccines to be used have been developed and manufactured by GSK Biologicals.

The Quality Control Standards and Requirements for each candidate vaccine are described in separate Quality Assurance documents (e.g. release protocols, certificate of analysis) and the required approvals have been obtained.

The vaccines are labelled and packed according to applicable regulatory requirements.

Table 14 Study vaccines

| Treatment name | Vaccine/ product name | Formulation | Presentation | Volume to be administered | No doses |
|--------------------------------|-----------------------|---|--|---------------------------|----------|
| 10-10-10/ Plain | NTHi-Mcat 10-10-10 | PD=10 µg; PE-PilA=10 µg; UspA2=10 µg | Freeze-dried antigens in monodose vial | 0.5 ml | 2 |
| | NaCl | NaCl=150mM | Liquid in monodose vial | | |
| 10-10- 10/AS01 _E | NTHi-Mcat 10-10-10 | PD=10 µg; PE-PilA=10 µg; UspA2=10 µg | Freeze-dried antigens in monodose vial | 0.5 ml | 2 |
| | AS01 _E | MPL=25 µg; QS21=25 µg; Liposomes | Liquid in monodose vial | | |
| 10-10- 3/AS01 _E | NTHi-Mcat 30-30-10 | * PD=30 µg; PE-PilA=30 µg; UspA2=10 µg | Freeze-dried antigens in monodose vial | 0.5 ml | 2 |
| | AS01 _E | MPL=25 µg; QS21=25 µg; Liposomes | Liquid in monodose vial | | |
| Placebo | NaCl | NaCl=150mM | Liquid in monodose vial | 0.5 ml | 2 |

*Vials containing 37.5 µg, 37.5 µg and 12.5 µg of freeze-dried PD, PE-PilA and UspA2, respectively, will be diluted in three volumes of AS01_E (total of ~1875 µL). 0.5 mL will be administered.

6.2. Storage and handling of study vaccines

The study vaccines must be stored at the respective label storage temperature conditions in a safe and locked place. Access to the storage space should be limited to authorized study personnel. The storage conditions will be assessed during pre-study activities under the responsibility of the sponsor study contact. The storage temperature should be continuously monitored with calibrated (if not validated) temperature monitoring device(s) and recorded. Refer to the Module on Clinical Trial Supplies in the SPM for more details on storage of the study vaccines.

Temperature excursions must be reported in degree Celsius.

Any temperature excursion outside the range of 0.0 to +8.0°C (for +2 to +8°C label storage condition) impacting investigational medicinal products (IMPs) must be reported

in the appropriate (electronic) temperature excursion decision form ([e]TDF). The impacted IMPs must not be used and must be stored in quarantine at label temperature conditions until usage approval has been obtained from the sponsor.

In case of temperature excursion below +2.0°C down to 0.0°C impacting IMP(s) there is no need to report in (e)TDF, but adequate actions must be taken to restore the +2 to +8°C label storage temperature conditions. The impacted IMP(s) may still be administered, but the site should avoid re-occurrence of such temperature excursion. Refer to the Module on Clinical Trial Supplies in the SPM for more details on actions to take.

Refer to the Module on Clinical Trial Supplies in the SPM for details and instructions on the temperature excursion reporting and usage decision process, packaging and accountability of the study vaccines.

6.3. Dosage and administration of study vaccines

Table 15 Dosage and administration

| Type of contact and time point | Volume to be administered | Study Group | Treatment name | Route ¹ | Site | Side ² | | | |
|--------------------------------|---------------------------|-------------|-----------------------------|--------------------|---------|-------------------|--|--|--|
| Visit 1 (Day 0) | 0.5mL | 10-10-10 | 10-10-10/Plain | IM | Deltoid | Non-dominant | | | |
| | | 10-10-10-AS | 10-10-10/AS01 _E | | | | | | |
| | | 10-10-3-AS | 10-10-3/AS01 _E * | | | | | | |
| | | PLACE1 | Placebo | | | | | | |
| | | PLACE2 | | | | | | | |
| Visit 4 (Day 60) | 0.5mL | 10-10-10 | 10-10-10/Plain | IM | Deltoid | Non-dominant | | | |
| | | 10-10-10-AS | 10-10-10/AS01 _E | | | | | | |
| | | 10-10-3-AS | 10-10-3/AS01 _E * | | | | | | |
| | | PLACE1 | Placebo | | | | | | |
| | | PLACE2 | | | | | | | |

¹ Intramuscular (IM)

² The deltoid of the non-dominant arm is the preferred side of injection. In case it is not possible to inject in the non-dominant arm, an injection in the dominant arm may be performed.

* Vials containing 37.5 µg, 37.5 µg and 12.5 µg of freeze-dried PD, PE-PiA and UspA2, respectively, will be diluted in three volumes of AS01_E (~1875 µL). 0.5mL will be administered.

6.3.1. Instructions for study vaccine preparation and administration

GSK Biologicals' NTHi-Mcat investigational vaccines should be prepared maximum two hours prior to injection.

6.3.1.1. Instructions for reconstitution and administration of investigational 10-10-10/Plain or 10-10-10/AS01_E vaccines

The vaccine formulations 10-10-10/Plain and 10-10-10/AS01_E will be delivered as two separate monodose vials, one containing the freeze-dried cake (NTHi-Mcat 10-10-10) and the other one containing the diluent (saline or AS01_E adjuvant). The entire content of the liquid-containing vial (diluent) will be injected into the vial of the freeze-dried cake. Following complete reconstitution of the cake by gentle rotations, the entire volume of this final reconstituted formulation will be withdrawn into a syringe. The excess volume

together with any remaining air bubbles will be expelled, so that a volume of 0.5 mL is finally administered to the subject. The content of the syringe will be masked with an opaque injection label to ensure blinding of the subjects. A small gap at the top of the syringe should be left in order to allow the administrator of the vaccine to check the liquid before injection. Finally, intramuscular injection of 0.5 mL should be done into the deltoid of the non-dominant arm. In case it is not possible to inject in the non-dominant arm, an injection in the dominant arm may be performed.

6.3.1.2. Instructions for reconstitution and administration of investigational 10-10-3/AS01_E vaccine

The vaccine formulation 10-10-3/AS01_E will be delivered as four separate monodose vials, one containing the freeze-dried cake (NTHi-Mcat 30-30-10) and three vials containing the AS01_E adjuvant. The whole content of each of the three vials of AS01_E must be used to reconstitute one vial of NTHi-Mcat 30-30-10 freeze-dried cake. Complete reconstitution of the cake by gentle rotations needs to be achieved before vaccine can be retrieved for injection. A suitable volume of this final reconstituted formulation will be withdrawn in a new calibrated syringe. The excess volume together with any remaining air bubbles will be expelled, so that a volume of 0.5 mL is administered to the subject. The content of the syringe should be masked with an opaque injection label to ensure blinding of the subjects. A small gap at the top of the syringe should be left in order to allow the administrator of the vaccine to check the liquid before injection. Finally, intramuscular injection of 0.5 mL should be done into the deltoid of the non-dominant arm. In case it is not possible to inject in the non-dominant arm, an injection in the dominant arm may be performed.

Please refer to the SPM for more detailed instructions on study vaccines preparation (e.g. needles and syringes used for reconstitution).

6.3.1.3. Instructions for preparation and administration of saline placebo

The saline solution will be delivered in a monodose vial, ready to use. The saline solution is transparent. If turbid or a precipitation is observed, the vial should not be used. Air bubbles and any excess volume have to be expelled. The content of the syringe will be masked with an opaque injection label to ensure blinding of the subjects. A small gap at the top of the syringe should be left in order to allow the administrator to check the liquid before injection. Finally, intramuscular injection of 0.5 mL should be done into the deltoid of the non-dominant arm. In case it is not possible to inject in the non-dominant arm, an injection in the dominant arm may be performed.

Please refer to the SPM for more detailed instructions on study vaccines administration.

6.4. Replacement of unusable vaccine doses

In addition to the vaccine doses provided for the planned number of subjects (including over-randomisation when applicable), at least 20% additional vaccine doses will be supplied to replace those that are unusable.

The investigator will use SBIR to obtain the replacement vial number. The replacement numbers will be allocated by dose. The system will ensure, in a blinded manner, that the replacement vial matches the formulation the subject was assigned to by randomisation.

6.5. Contraindications to subsequent vaccination

The following events constitute absolute contraindications to further administration of the NTHi-Mcat investigational vaccines. If any of these events occur during the study, the subject must not receive vaccine Dose 2 but may continue other study procedures at the discretion of the investigator (see Section 8.5).

- Anaphylaxis following the administration of vaccine.
- Pregnancy.
- Any confirmed or suspected immunosuppressive or immunodeficient condition, including HIV infection.
- Current auto-immune disease.

The following events constitute contraindications to administration of the NTHi-Mcat investigational vaccines at that point in time; if any of these events occur at the time scheduled for vaccination, the subject may be vaccinated at a later date, within the time window specified in the protocol (see [Table 7](#)), or the subject may be withdrawn at the discretion of the investigator (see Section 8.5).

- Acute disease and/or fever at the time of vaccination.
 - Fever is defined as a temperature $\geq 37.5^{\circ}\text{C}$ for oral or axillary route. The preferred route for recording temperature in this study will be oral.
 - Subjects with a minor illness (such as mild diarrhoea, mild upper respiratory infection) without fever can be administered all vaccines.

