8.2. Events or outcomes not qualifying as adverse events or serious adverse events

Pregnancy

Female subjects who are pregnant or lactating at the time of vaccination must not receive additional doses of study vaccines but may continue other study procedures at the discretion of the investigator.

While pregnancy itself is not considered an AE or SAE, any adverse pregnancy outcome or complication or elective termination of a pregnancy for medical reasons will be recorded and reported as an AE or a SAE.

Note: The pregnancy itself should always be recorded on an electronic pregnancy report.

The following should always be considered as SAE and will be reported as described in Sections 8.4.1 and 8.4.3:

- Spontaneous pregnancy loss, including:
 - spontaneous abortion, (spontaneous pregnancy loss before/at 22 weeks of gestation)
 - ectopic and molar pregnancy
 - stillbirth (intrauterine death of foetus after 22 weeks of gestation).

Note: the 22 weeks cut-off in gestational age is based on WHO-ICD 10 noted in the EMA Guideline on pregnancy exposure [[EMA](#), 2006]. It is recognized that national regulations might be different.

- Any early neonatal death (i.e. death of a live born infant occurring within the first 7 days of life).

- Any congenital anomaly or birth defect (as per [CDC MACDP] guidelines) identified in the offspring of a study subject (either during pregnancy, at birth or later) regardless of whether the foetus is delivered dead or alive. This includes anomalies identified by prenatal ultrasound, amniocentesis or examination of the products of conception after elective or spontaneous abortion.

Furthermore, any SAE occurring as a result of a post-study pregnancy AND considered by the investigator to be reasonably related to the investigational vaccines will be reported to GSK Biologicals as described in Section 8.4.3. While the investigator is not obligated to actively seek this information from former study participants, he/she may learn of a pregnancy through spontaneous reporting.

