8.10.2.2. Process for the suspension of vaccination and/or study modification

In the event that a safety signal is observed, GSK Biologicals' VSMB might decide to suspend further vaccinations in all groups or in selected groups.

In case the vaccination is suspended:

- Subjects who signed an informed consent but have not received any study vaccine will be informed that their study participation will be stopped.
- For all other subjects, all visits will continue as planned for evaluation of the safety and immunogenicity of the vaccine except that Visit 5 on Day 67 will be cancelled if no vaccine dose is administered at Visit 4 on Day 60.

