9.2.2. Subject withdrawal from investigational vaccine

A ‘withdrawal’ from the investigational vaccine refers to any subject who does not receive the complete treatment, i.e. when no further planned dose is administered from the date of withdrawal. A subject withdrawn from the investigational vaccine may not necessarily be withdrawn from the study as further study procedures or follow-up may be performed (safety or immunogenicity) if planned in the study protocol.

Information relative to premature discontinuation of the investigational vaccine will be documented on the Vaccine Administration page/screen of the eCRF. The investigator will document whether the decision to discontinue further vaccination/treatment was made by the subject himself/herself, or by the investigator, as well as which of the following possible reasons was responsible for withdrawal:

- SAE.
- Non-SAE.
- Other (specify).

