10. STATISTICAL METHODS

10.1. Primary endpoints

- Occurrence of each solicited local and general AE, during a 7-day follow-up period (i.e. day of vaccination and 6 subsequent days) post-Dose 1 and post-Dose 2, in all subjects, in all vaccine groups.
- Occurrence of any unsolicited AEs, during a 30-day follow-up period (i.e. day of vaccination and 29 subsequent days) post-Dose 1 and post-Dose 2, in all subjects, in all vaccine groups.

- Occurrence of haematological and biochemical laboratory abnormalities, after vaccination, in all subjects, in all vaccine groups:
 - Any haematological (RBC, WBC and differential count, platelets count and haemoglobin level) or biochemical (ALT, AST and creatinine) laboratory abnormality on Day 7, Day 60, Day 67, Day 210 and Day 420.
- Occurrence of any SAE, occurring from first vaccination (Day 0) to study conclusion (Day 420) in all subjects, in all vaccine groups.
- Occurrence of any pIMD occurring from first vaccination (Day 0) to study conclusion (Day 420) in all subjects, in all vaccine groups.

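### After an individual Dose 2 stop, scheduled safety follow-up is discretionary (Protocol 6.5, 8.2), but it is kept when vaccination is suspended (8.10.2.2), so late primary safety data can be missing for safety-related reasons

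*Protocol*

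**What the plan says.** The relevant provisions are spread over several protocol sections.

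- **6.5, absolute contraindications** (anaphylaxis, pregnancy, immunosuppression or immunodeficiency, current auto-immune disease): "the subject must not receive vaccine Dose 2 but may continue other study procedures at the discretion of the investigator". The sentence then points to 8.5.
- **8.2, pregnancy and lactation**: such subjects "must not receive additional doses of study vaccines but may continue other study procedures at the discretion of the investigator".
- **6.5, temporary contraindications** (acute disease or fever on the day): the dose may be given later within the window, "or the subject may be withdrawn at the discretion of the investigator". Sections 5.6.12 and 5.6.15 mention only rescheduling. Table 7 puts Visit 4 at Day 60 to 70.
- **8.10.2.2, vaccination suspended**: "For all other subjects, all visits will continue as planned for evaluation of the safety and immunogenicity of the vaccine". The one exception is that Visit 5 is cancelled when no dose is given at Visit 4.
- **9.2.2** separates stopping the vaccine from leaving the study. It permits further follow-up where the protocol plans it, but does not require it.
- **10.1** defines a primary endpoint as "Occurrence of any pIMD occurring from first vaccination (Day 0) to study conclusion (Day 420) in all subjects, in all vaccine groups". SAEs have the same span, and laboratory abnormalities are assessed on Days 7, 60, 67, 210 and 420.

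**The concern.** A subject who has had Dose 1 and will not have Dose 2 meets one follow-up rule if the study is paused and another if the reason is personal. The personal reasons include safety outcomes. Anaphylaxis is one, and current auto-immune disease overlaps with the pIMD list in Table 18. Vaccine-induced autoimmune disease is also the potential risk named in the risk table of 1.3.1.

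If the investigator does not continue such a subject, observation can end because of something that happened after Dose 1. Missing late data would then depend on safety history, while the primary endpoints claim coverage of all subjects to Day 420.

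**Working it through.** **1. The rules side by side**, for a subject with one dose:

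| Reason for no Dose 2 | Scheduled visits afterwards | Place |
|---|---|---|
| Suspension | All kept except Visit 5 | 8.10.2.2 |
| Absolute contraindication | Investigator's discretion | 6.5 |
| Pregnancy or lactation | Investigator's discretion | 8.2 (pregnancy also 6.5) |
| Acute disease or fever at Visit 4 | Reschedule, or withdrawal of unstated kind | 6.5; 5.6.12 has rescheduling only |

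**2. What is secured in any case.** 8.5.1.1 reviews open SAEs and pIMDs at later visits or contacts to study end. 8.5.1.2 follows subjects with an SAE or pIMD, or withdrawn for an AE, until that event settles. 8.5.2 follows pregnancies to outcome. 10.4.1 keeps anyone with one dose in the total vaccinated cohort, and 9.2.1 uses all data to last contact.

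**3. What is not secured.** 8.5 deals with events already known and with pregnancies. It does not require a scheduled blood draw or a search for a new SAE or pIMD. After discharge, 8.3.2 says the investigator need not actively look for events.

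For a subject released at Visit 4 with Day 60 bloods taken:
- SAE/pIMD collection time lost: (420 − 60)/420 = 360/420 = 86%.
- Laboratory time points lost relative to 8.10.2.2: Day 210 and Day 420, which is 2 of 5. Day 67 falls away under 8.10.2.2 as well. A subject released earlier could also miss Day 60.

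**4. Precision.** The chance of seeing at least one event with true rate p among n subjects is 1 − (1 − p)^n. With p = 5% and n = 30, this is 1 − 0.95^30 = 78.5%, which reproduces the figure in 10.3. The upper exact limit for 0/15 is 1 − 0.025^(1/15) = 21.8%, as in Table 23. The documents give no number of contraindicated subjects, so I assume 1, 2 or 3 lost per group:

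| Lost | Detection of a 5% event, from n = 30 | From n = 15 |
|---|---|---|
| 0 | 78.5% | 53.7% |
| 1 | 77.4% | 51.2% |
| 2 | 76.2% | 48.7% |
| 3 | 75.0% | 46.0% |

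**5. Possible bias.** No missing-data rule is given for SAEs, pIMDs or laboratory results. The rule in 10.5 that no report means no event covers unsolicited symptoms and concomitant products only. My reading is that a lost subject would count as free of later SAEs and pIMDs, because 10.6.2 reports the number of subjects with such an event. On that reading, if every lost subject had one unseen later event (exact 95% CIs):

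| Lost | Shown, n = 30 | Worst case, n = 30 | Shown, n = 15 | Worst case, n = 15 |
|---|---|---|---|---|
| 1 | 0/30 (0–11.6%) | 1/30 = 3.3% (0.1–17.2%) | 0/15 (0–21.8%) | 1/15 = 6.7% (0.2–31.9%) |
| 2 | 0/30 (0–11.6%) | 2/30 = 6.7% (0.8–22.1%) | 0/15 (0–21.8%) | 2/15 = 13.3% (1.7–40.5%) |
| 3 | 0/30 (0–11.6%) | 3/30 = 10.0% (2.1–26.5%) | 0/15 (0–21.8%) | 3/15 = 20.0% (4.3–48.1%) |

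These are bounds, not expectations. The maximum laboratory grade to Visit 8 (10.6.2) is affected in a similar way, since a subject without late bloods contributes a maximum over fewer draws.

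**The case against.** The strongest reply is that little is left to discretion. The 6.5 sentence itself points to 8.5, which is mandatory. 8.3.1 keeps SAE and pIMD collection open to study conclusion. The schedule tables apply to every subject, Table 8 lists the Day 210 and Day 420 bloods for all enrolled subjects, and 3.1 rules out waivers. A suspension is a study-level decision and a contraindication an individual medical one, so different latitude could be deliberate. The cases also overlap: one life-threatening SAE meets holding rule 1a, and if vaccination then stays suspended, 8.10.2.2 keeps that subject's visits.

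Much of this stands. A reader might infer that affected subjects drop out of the primary safety analysis. They do not: they remain in the total vaccinated cohort, and a triggering SAE or pIMD is recorded and counted. A reader might also infer heavier loss in the adjuvanted groups, and so a vaccine that looks safer than it is. No document supports that. Ordinary Grade 3 reactogenicity does not bar Dose 2, fever counts only at the vaccination visit, and 1.3.1 reports no confirmed autoimmune signal so far.

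The gap in scheduled data is not answered. The general schedule and the specific discretion in 6.5 and 8.2 point in different directions, and a site would reasonably follow the specific sentence. The reviews in 8.5.1.1 take place at visits or contacts, and it is the scheduled visits that become optional.

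**Conclusion.** The inconsistency is real and unreconciled, but narrow. Scheduled procedures after an individual Dose 2 stop are discretionary, whereas the same visits are kept under a suspension. The exposed data are later new SAEs and pIMDs, and the Day 210 and Day 420 safety bloods.

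Few subjects are likely to be affected, although the documents give no count. On the assumed loss of 1 to 3 of 30, detection of a 5% event falls by 1.1 to 3.5 points, which is minor. Possible informative loss matters more, because the trigger can itself be a safety event and the endpoint is defined in all subjects. Its direction and size cannot be derived from the documents.

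The main immunogenicity analysis is hardly touched, since the according-to-protocol cohort already requires compliance with the vaccination schedule. This is a cheap improvement worth making, not a defect that undermines a descriptive Phase I study.

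**What to change.** Reconcile 6.5, 8.2, 8.5, 8.10.2.2 and 9.2.2 on data collection:

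- Any subject with at least one dose who does not receive Dose 2 stays in the study for the safety data collection already scheduled: SAE and pIMD recording, and Day 210 and Day 420 bloods where medically acceptable. Immunogenicity sampling also continues to Day 420. Withdrawal of consent ends this.
- State in 6.5 whether withdrawal after acute disease or fever means from the vaccine or from the study, and align it with 5.6.12 and 5.6.15.

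Who may receive Dose 2, and how any event is managed, are left as they are. The cost is protocol wording, because the visits already exist. The downside is slightly less flexibility for sites.
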